9.7 Adverse Event Coding

Adverse Events will be categorized using the Medical Dictionary for Regulatory Activities (MedDRA) coding guidelines.

9.8 Independent Data Review

The Sponsor will establish an Independent Data Reviewer (IDR). The IDR will provide external oversight and review for potential safety concerns. The IDR is a physician expert in interventional cardiac therapy who is not participating in the trial and has no other affiliation with W. L. Gore & Associates, Inc.

During the course of the study, the IDR will review aggregate accumulating safety data to monitor for the incidence of serious adverse events and other trends that would warrant modification or termination of the study.

The IDR will review the overall safety data at regular intervals. The IDR responsibilities and operating procedures will be outlined in the IDR charter.

Any IDR recommendations for study modification or termination because of concerns over subject safety or issues relating to data monitoring or quality control will be submitted in writing to the Sponsor for consideration. However, if the IDR at any time determines that a potential serious risk exists to subjects in the study, the IDR will immediately notify the Sponsor.

10.0 Statistical Analysis

10.1 Primary Study Hypotheses

This study is designed to test the null hypothesis that the Clinical Success rate at 6 months when using the GORE® Septal Occluder is inferior to the

CONFIDENTIAL INFORMATION

Clinical Success rate at 6 months when using the GORE® HELEX® Septal Occluder device; versus the alternative hypothesis that the Clinical Success rate at 6 months when using the GORE® Septal Occluder is not inferior to the Clinical Success rate at 6 months when using the GORE® HELEX® Septal Occluder device.

The hypotheses are specified as follows:

$$H_0 : P_c - P_T \geq \Delta$$

$$H_A : P_c - P_T < \Delta$$

where:

P_c = the Clinical Success rate at 6 months when using the GORE® HELEX Septal Occluder (control arm)

P_T = the Clinical Success rate at 6 months when using the GORE® Septal Occluder (test arm)

Δ = the non-inferiority margin

10.2 Sample Size Assumptions

The safety and efficacy of the GORE® Septal Occluder will be evaluated by comparing this device to the currently marketed GORE® HELEX® Septal Occluder. To develop a control population for comparison to the GORE® Septal Occluder, an analysis of previous GORE® HELEX® Septal Occluder clinical studies was evaluated. The studies utilized included the HELEX® Device Continued Access Study (HLX 03-01) and HELEX® Device Post Approval Study (PAS HLX 06-04) as these were studies of the currently marketed implantable portion of the HELEX device (subsequent modifications to the delivery system have been made). The subject population in the HELEX device studies was limited to those subjects who would satisfy the defect size criteria for this study, specifically with defects ≤ 17 mm.

Table 10.2.1 presents the outcomes from the analysis of the HELEX device studies. Using the primary endpoint definition described in Section 3.2.3, the composite Clinical Success rate in the HELEX device studies was 86.6%.

Table 10.2.1
Composite Clinical Success with the GORE® HELEX Septal Occluder
GORE® HELEX Device Continued Access and Post-Approval Studies

	GORE® HELEX Septal Occluder
Subjects with Deployment Attempt	
Procedure Technical Success	
Implant Successful	
Implant Unsuccessful	

CONFIDENTIAL INFORMATION

Safety Outcomes at 6 Months	
Serious AE: Day 0-30	[REDACTED]
Device Embolization	[REDACTED]
Device Removal	[REDACTED]
Other ASD Reintervention	[REDACTED]
Other Serious Adverse Event	[REDACTED]
Device Embolization: Day 31-182	[REDACTED]
Device Removal: Day 31-182	[REDACTED]
Other ASD Reintervention: Day 31-182	[REDACTED]
Overall	[REDACTED]
Defect Closure Status at 6 Months (Core Lab)	
Occluded	[REDACTED]
Clinically Insignificant	[REDACTED]
Clinically Significant	[REDACTED]
Not Completed	[REDACTED]
Composite Clinical Success at 6 Months	
Success	[REDACTED]
Failure	[REDACTED]
Not Evaluated	[REDACTED]

10.3

Non-Inferiority Margin

The 6-month composite Clinical Success rate for the GORE® Septal Occluder will be considered non-inferior to the 6-month composite Clinical Success rate for the GORE® HELEX® Septal Occluder if the difference in rates ($P_c - P_T$) is less than 10%. This non-inferiority margin is based on (1) the 95% confidence interval lower bound for the estimated 6-month composite Clinical Success rate for the HELEX device (82%) and (2) a worst-case analysis of the 6-month composite Clinical Success rate for the HELEX device (81%, assuming the 18 subjects with missing echo evaluations were failures).

10.4

Sample Size Determination

Sample size for the Test group was estimated with Power and Sample Size (PASS) 2008 (Kaysville, UT) using a two-sample, non-inferiority binomial proportions test with the following assumptions:

Type I error (alpha)	0.05
1-Type II error (power)	≥0.86
N_c (HELEX sample size)	253
P_c (HELEX)	86.6%
P_T (GSO)	86.6%
Non-Inferiority margin	10%

Based on these conditions, it was estimated that 135 subjects with primary endpoint data will be required. To allow for an anticipated withdrawal and

CONFIDENTIAL INFORMATION

lost to follow-up rate of up to 10% before the 6-month endpoint, a minimum of 150 subjects will be enrolled in the study.

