Subjects with unsuccessful placement of a GORE® Septal Occluder (no study device implanted at conclusion of index procedure) will be followed through 30 days post index procedure. Subjects will be contacted by phone at 30 days for follow-up; upon completion of the telephone follow-up Case Report Form (CRF) at the 30-day Unsuccessful Implant interval, subject is discontinued from the study. These subjects will be considered enrolled and a technical failure for purposes of study analysis.

CONFIDENTIAL INFORMATION

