10.6.2 Analysis Populations

The analysis populations for the study are:

- Per-Protocol (primary analysis population) – this population will include enrolled subjects who had no inclusion/exclusion

CONFIDENTIAL INFORMATION

violations and who complete evaluation through the 6-month follow-up.

- Intent-to-treat – this population will include all enrolled subjects.

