10.6.3 Statistical Analysis of Primary Endpoint

The primary endpoint analysis will be a comparison of the proportion of subjects who meet the composite Clinical Success requirements through the 6-month follow-up between the study population and the historical control population of GORE® HELEX Septal Occluder studies. The primary analysis population will be the per-protocol population. The primary endpoint will be compared using a two-sample binomial proportions test with a non-inferiority margin of 10%. In statistical terms:

$$z = \frac{p_C - p_T - \Delta}{\sqrt{\frac{p_C(1-p_C)}{n_C} + \frac{p_T(1-p_T)}{n_T}}}$$

where:

p_C = observed Clinical Success proportion at 6 months in control group

n_C = number of subjects with primary endpoint evaluation in control group

p_T = observed Clinical Success proportion at 6 months in test group

n_T = number of subjects with primary endpoint evaluation in test group

The test statistic z is assumed to have a standard Normal distribution. Based on the alpha ≤ 0.05 criterion, a result of $z < -1.64$ will result in rejection of the null hypothesis in favor of the alternative hypothesis and a conclusion that the GORE® Septal Occluder is not inferior to the current GORE® HELEX Septal Occluder.

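### The only non-inferiority test is run on 6-month completers: read literally, it drops known device failures, and the defined intent-to-treat population has no analysis and no missing-data rule

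*Combined protocol and SAP*

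**What the plan says.** **Margin and sample size (10.3, 10.4).** The margin is 10 percentage points. Two HELEX figures are given for it. The first is a confidence bound of 82%: "This non-inferiority margin is based on (1) the 95% confidence interval lower bound for the estimated 6-month composite Clinical Success rate". The second is a worst case: "HELEX device (81%, assuming the 18 subjects with missing echo evaluations were failures". The sample size section requires 135 evaluable subjects and enrols at least 150, to cover a withdrawal and "lost to follow-up rate of up to 10% before the 6-month endpoint".

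**Populations (10.6.2).** Per-protocol means no eligibility violations and subjects "who complete evaluation through the 6-month follow-up". For intent-to-treat, "this population will include all enrolled subjects".

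**Test (10.6.3).** "The primary analysis population will be the per-protocol population". The test denominator is defined as "n_T = number of subjects with primary endpoint evaluation in test group", and the HELEX denominator is defined in the same way. Non-inferiority is concluded if z < -1.64. No analysis of the primary endpoint is assigned to the intent-to-treat population, and no rule is given for a missing 6-month status.

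**Subjects who leave early.** After an unsuccessful implant, follow-up ends with a 30-day telephone call (5.4.6). The same section says: "These subjects will be considered enrolled and a technical failure for purposes of study analysis". A subject whose device is later removed is discontinued (5.4.9, 5.5). Under 3.2.1 the composite needs successful deployment and retention, and freedom from embolization, removal or reintervention through 6 months. Both groups have therefore already failed it.

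**The concern.** Two gaps meet in the one confirmatory test.

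First, the per-protocol wording selects on an event that some failures cannot reach. A subject with no device, or with the device removed at month 3, does not complete the 6-month evaluation. Dropping that subject removes a certain failure from the test-device count. The sentence in 5.4.6 points the other way for failed implants. Nothing comparable protects subjects with early device removal.

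Second, 10.3 recognises that missing HELEX echoes could hide failures and shows what happens if they do. The plan never asks the same question of the test device. Up to 10% loss is met only by enrolling more subjects, which restores precision but says nothing about the outcomes of those lost.

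At stake is the final non-inferiority conclusion. The 30-day and PMA analyses are descriptive (10.6.1) and involve no test.

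**Working it through.** **Inputs.** HELEX rate 86.6%, N_c = 253, margin 0.10, one-sided alpha 0.05, 135 evaluable, 150 enrolled (10.2 to 10.4). Critical value -1.64 (10.6.3).

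**Reproducing the plan's figures.**
- HELEX counts, inferred because Table 10.2.1 is redacted: 219/253 = 86.6%. Wald lower bound: 0.8656 - 1.96 × sqrt(0.8656 × 0.1344 / 253) = 82.4%. Worst case: 219/(253 + 18) = 219/271 = 80.8%. These match 86.6%, 82% and 81%, so the 18 lie outside the 253.
- Power at 135: SE = sqrt(0.866 × 0.134 × (1/253 + 1/135)) = 0.0363, and Phi(0.10/0.0363 - 1.645) = 0.866. Enrolment: 135/0.9 = 150.

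**Statistic (10.6.3).** z = (p_C - p_T - 0.10)/SE, with SE = sqrt[p_C(1 - p_C)/n_C + p_T(1 - p_T)/n_T].

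**A. Known failures dropped.** The documents give no expected number of failed implants or early removals. Take 8 of 150 as an illustration, with no other missing data and HELEX at 219/253.

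| Test result | p_C - p_T | SE | z | Outcome |
|---|---|---|---|---|
| 118/142 (8 dropped) | 0.0346 | 0.0381 | -1.72 | pass |
| 118/150 (8 counted) | 0.0789 | 0.0397 | -0.53 | fail |
| 124/150 | 0.0389 | 0.0376 | -1.62 | fail |
| 125/150 | 0.0323 | 0.0372 | -1.82 | pass (minimum) |

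Effect on false passes: take a device exactly at the margin, true success 76.6% of all enrolled, and drop a fraction d of the 150 as known failures. The apparent rate is 0.766/(1 - d), and the pass probability is approximately Phi[(0.10 - (0.866 - 0.766/(1 - d)))/SE - 1.64].

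| d | Apparent rate | SE | Pass probability |
|---|---|---|---|
| 0 | 76.6% | 0.0407 | 5% |
| 1% | 77.4% | 0.0405 | 7% |
| 2% | 78.2% | 0.0402 | 11% |
| 3% | 79.0% | 0.0400 | 15% |
| 5% | 80.6% | 0.0394 | 27% |

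**B. Missing status counted as failure in both arms.** Take 15 of 150 missing, the most that 10.4 allows for.

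| Comparison | p_C - p_T | SE | z | Outcome |
|---|---|---|---|---|
| 112/135 v 219/253 (as planned; minimum pass) | 0.0360 | 0.0388 | -1.65 | pass |
| 112/150 v 219/271 | 0.0615 | 0.0428 | -0.90 | fail |
| 116/150 v 219/271 | 0.0348 | 0.0417 | -1.56 | fail |
| 117/150 v 219/271 | 0.0281 | 0.0414 | -1.74 | pass (minimum) |

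For 112/150 the one-sided 95% upper limit of the loss is 0.0615 + 1.645 × 0.0428 = 13.2 points. Completer results of 112 to 116 out of 135 therefore change verdict. With 40 of 400 missing, so do 294 to 304 out of 360 (294/400 v 219/271: z = -0.83, upper limit 12.7 points).

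**The case against.** **Failed implants may already be covered.** Section 5.4.6 counts them as technical failures for analysis, and deployment is the first criterion of the composite. A sensible analyst would probably keep them. That stands as far as it goes, but it contradicts the literal per-protocol definition and does not reach early removals under 5.4.9 and 5.5.

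**The arms are treated alike within the test.** A reader might infer that the test drops missing subjects on one side only. It does not: both denominators are evaluated subjects, and the 253 already excludes the 18. The mismatch is between the reasoning in 10.3 and the test in 10.6.3.

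**The margin.** A reader might infer that the worst case produced an overly generous 10 points. The documents do not support this. The worst case is one of two grounds, and the two lie only 4.6 and 5.6 points below 86.6%. Nothing shows that 10 points is too wide.

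**Random missingness.** A reader might also infer that the results that change verdict in part B are false passes. If loss is unrelated to outcome, the completer comparison is unbiased and false passes stay near 5%. Counting missing as failure then simply penalises the arm with more missing (10% against 18/271 = 6.6%). A device whose true loss is under 10 points is non-inferior by the plan's own definition, so its passing is no error. Part B shows that the conclusion depends on unobserved subjects, not that it is wrong.

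**Conclusion.** The concern holds in two parts.

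The stronger part is the known failures. If the literal per-protocol wording is followed, bias runs towards the test device and does not rest on any guess about unobserved outcomes. At 5% of 150 dropped, a device exactly at the margin passes about 27% of the time instead of about 5%; at 1% it passes about 7%. The size depends on a failure rate that the documents do not give. It also assumes that the HELEX 219/253 keeps its own known failures. The row headings of Table 10.2.1, which start from deployment attempts and list unsuccessful implants and removals, suggest that it does, but the counts are redacted. If HELEX dropped them too, the bias would partly cancel.

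The second part is that no sensitivity analysis for missing 6-month status is specified, although the intent-to-treat population exists and 10.3 supplies the worst-case method. At the plan's 10% allowance the two analyses disagree for 112 to 116 successes out of 135. This part rests on the inferred 219 and assumes no exclusions for eligibility.

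**What to change.** 1. **10.6.2 and 10.6.3:** state that any subject already known to have failed a component of the composite (failed implant, SAE through 30 days, device event through 6 months) counts as a failure in the primary analysis, whether or not the 6-month evaluation was done. Handle HELEX in the same way. Reconcile this wording with 5.4.6, 5.4.9 and 5.5.
2. **10.6.3:** pre-specify an intent-to-treat analysis of the primary endpoint, with the confidence interval for the difference. Either count missing 6-month status as failure in both arms (HELEX 219/271, to be confirmed from the sponsor's unredacted table) or use a tipping-point analysis. Report it beside the primary result, and qualify the non-inferiority conclusion if the two disagree.

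The cost is a few sentences, one more analysis and a possibly less favourable result. No visits or data are added, and the margin and the 150 to 400 enrolment stay.

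The intent-to-treat analysis is not proposed as a second pass/fail test. For equal devices with 15 of 150 missing at random and HELEX held at its inferred counts, requiring both to pass would cut power from 0.911 to 0.553, against the plan's target of at least 0.86. That is a debatable trade-off, which reporting both results avoids.

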10.5 Study Enrollment

Enrollment in the GORE® Septal Occluder study will occur in three phases:

1. Pivotal cohort of 50 subjects from a maximum of 10 sites.
Enrollment in this phase will begin upon Investigational Device Exemption (IDE) approval. Upon completion of 6 month follow up for all 50 subjects, a submission will be made to FDA for Pre-Market Approval (PMA).
2. Continued Access cohort of 100 – 350 subjects from 10 – 21 (up to 11 additional) sites. Enrollment in this phase will begin after FDA acceptance of 30-day safety analysis on the Pivotal cohort.
3. Post Approval cohort of subjects will be enrolled depending on the number achieved in Continued Access upon PMA approval.
Enrollment in this phase will begin after FDA pre-market approval for GORE® Septal Occluder. (Post Approval Study [PAS] subjects will be enrolled pursuant to the approval of this protocol and PMA.)

Total enrollment for the GORE® Septal Occluder study will be 150 – 400 subjects. All subjects will be enrolled and followed under the same criteria through the 36 months post index procedure.

10.6.2 Analysis Populations

The analysis populations for the study are:

- Per-Protocol (primary analysis population) – this population will include enrolled subjects who had no inclusion/exclusion

CONFIDENTIAL INFORMATION

violations and who complete evaluation through the 6-month follow-up.

- Intent-to-treat – this population will include all enrolled subjects.

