3.2 Study Endpoints

3.2.1 Primary Endpoint

The primary endpoint for the study is composite Clinical Success evaluated at 6 months post index procedure and is defined as satisfying all the following criteria:

1. Successful deployment and retention (at conclusion of index procedure) of a GORE® Septal Occluder
2. Freedom from:
 - any Serious Adverse Event (SAE) through 30 days post procedure
 - device events (post-procedure embolization, device removal, or other device reintervention) from completion of the implant procedure through the 6-month follow-up evaluation
3. A clinical residual defect status of completely occluded or clinically insignificant residual shunt at 6-month evaluation as determined by the Echo Core Lab (see Section 3.2.3)

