5.4.9 Reinterventions

Reinterventions to the study device (GORE® Septal Occluder) will be reported on the Intervention CRF. If the GORE® Septal Occluder is removed as part of the reintervention, then the subject is discontinued from the study. If the GORE® Septal Occluder remains implanted, then the subject will continue to be enrolled and will complete study follow-up as prescribed.

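### Taken at its word, the primary per-protocol population drops subjects who have already failed the composite endpoint (failed implants, embolizations and removals, early deaths)

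*Combined protocol and SAP*

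**What the plan says.** Section 10.6.2 defines two populations. The per-protocol set consists of enrolled subjects with no inclusion or exclusion "violations and who complete evaluation through the 6-month follow-up". The intent-to-treat set is everyone enrolled. Section 10.6.3 then states: "The primary analysis population will be the per-protocol population". It defines the test-arm denominator n_T as the "number of subjects with primary endpoint evaluation in test group". No primary-endpoint analysis is assigned to the intent-to-treat set, and 10.6.1 makes the two earlier analyses descriptive.

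Section 3.2.1 makes three things necessary for Clinical Success: a device deployed and retained at the end of the index procedure; freedom from any SAE through day 30 and from "device events (post-procedure embolization, device removal, or other device reintervention) from completion of the implant procedure through the 6-month follow-up evaluation"; and an acceptable core-lab shunt status at 6 months. A subject can therefore fail well before the 6-month visit.

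Other sections end follow-up for many of those subjects:

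- **Failed implants (5.4.6):** after the 30-day telephone contact the "subject is discontinued from the study. These subjects will be considered enrolled and a technical failure for purposes of study analysis".
- **Reintervention with device removal (5.4.9):** "then the subject is discontinued from the study". If the device stays in, "then the subject will continue to be enrolled and will complete study follow-up as prescribed".
- **Embolization or other loss of the device after the index procedure (5.5):** discontinued from further follow-up.
- **Death (5.7):** classed as a withdrawal. Under 9.4 an adverse event leading to death is an SAE.

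**The concern.** Completing the 6-month evaluation is a condition of entry to the primary analysis set, and several kinds of failure make it impossible to meet. Four groups are affected: failed implants; post-procedure embolizations and removals; deaths by day 30; and subjects with an SAE by day 30 who have no 6-month evaluation. Each is a failure under 3.2.1, and each would be left out because of, or after, that failure.

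The loss is partial. A subject with an early SAE who attends at 6 months, or one reintervened on with the device retained, stays in and counts as a failure. So component 1 of the composite and part of component 2 are affected.

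At stake is the study's single confirmatory conclusion. Removing failures from one side of a non-inferiority comparison raises that side's success rate and makes non-inferiority easier to claim. Two analysts following this plan could also arrive at different denominators.

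**Working it through.** **Inputs.** From 10.4: control n_C = 253, P_C = P_T = 86.6%, margin 10 points, alpha 0.05, power at least 0.86, 135 evaluable test subjects, and 150 enrolled after 10% loss. From 10.6.3: reject if z < -1.64, with

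z = (p_C − p_T − 0.10) / √[p_C(1−p_C)/n_C + p_T(1−p_T)/n_T].

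From 10.3: 18 HELEX subjects with missing echoes, and a worst-case rate of 81%. The component counts in Table 10.2.1 are redacted, so f, the share of subjects who are known failures and would be dropped, is an assumption shown over a range.

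**The plan's own figure.** The standard error is √[0.866 × 0.134 × (1/253 + 1/135)] = 0.0363. Power is Φ(0.10/0.0363 − 1.645) = 0.866 (0.856 by exact enumeration of two binomials). Enrollment is 135/0.9 = 150. The sample size reproduces, so the problem lies in the population definition and not in the arithmetic.

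**How HELEX appears to be scored.** 86.6% of 253 is about 219 successes (219/253 = 86.6%). Adding the 18 missing echoes gives 219/271 = 80.8%, which matches the stated 81%. Table 10.2.1 has rows for unsuccessful implants and removals, and lists failures apart from subjects not evaluated. This fits a control in which only subjects with missing echoes were left out and known failures were kept. The 219 and 271 are inferred.

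**Case A: HELEX keeps known failures and the test arm drops them.** Put the true rate among all subjects at the margin, 86.6% − 10 = 76.6%. After dropping, the test-arm rate is 0.766/(1−f) on n_T = base × (1−f), rounded. Exact probability of declaring non-inferiority:

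| f | Test-arm rate after dropping | Base 135 | Base 360 (90% of 400) |
|---|---|---|---|
| 0% | 76.6% | 5.8% | 4.9% |
| 1% | 77.4% | 8.2% | 8.1% |
| 2% | 78.2% | 11.5% | 12.6% |
| 3% | 79.0% | 15.6% | 19.2% |
| 5% | 80.6% | 27.6% | 37.8% |

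The 5.8% at f = 0 is the planned test's own small excess over 5%. From f = 2% upward the larger study has the higher error, because a fixed bias is set against a smaller standard error.

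**Case B: both sides drop known failures.** Take 86.6% as the control rate after exclusion, the same f on both sides, and a true all-subject difference of 10 points. Then P_T = [0.866(1−f) − 0.10]/(1−f). With base 135 the error is 5.5%, 5.3%, 5.0% and 4.7% at f = 1, 2, 3 and 5%; with base 360 it is 4.6%, 4.3%, 4.0% and 3.4%. There is no inflation.

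**Reversals against 219/253:**

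| Successes | Failures kept | Failures dropped |
|---|---|---|
| 111 | 111/135: z = -1.44, not shown | 111/133 (two dropped): z = -1.78, shown |
| 110 | 110/135: z = -1.24, not shown | 110/132 (three dropped): z = -1.74, shown |
| 108 | 108/135: z = -0.85, not shown | 108/130 (five dropped): z = -1.66, shown |

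**The case against.** The best defense is that the sponsor did not mean this. Section 5.4.6 treats failed implants as technical failures in the analysis. Excluding them would leave the deployment component almost nothing to measure. The wording of n_T can be read as covering anyone whose endpoint is determined, and a failed implant or a removal has a determined endpoint without an echo. The layout of Table 10.2.1 points the same way. On this view, completing evaluation means having a known outcome, and the defect is an ambiguity.

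Much of that is fair as a guess at intent, and for failed implants the text does conflict with itself. But 5.4.6 does not mention the per-protocol set, and no similar sentence covers embolizations, removals or early deaths. The n_T wording sits in the same section that imposes the per-protocol definition and does not override it.

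Two points about size also stand. The inflation requires HELEX to have kept its failures, which cannot be confirmed, and f is not given anywhere. The two-subject reversal is also a narrow case: with 135 subjects it occurs only at exactly 111 successes, which has a probability of about 3.2% at a true rate of 86.6% and 2.5% at 76.6%. It shows how sensitive the result is near the threshold, and does not mean a reversal is likely. Neither point makes the written rule correct.

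**Conclusion.** The concern holds. Followed as written, 10.6.2 removes known composite failures from the only hypothesis test, and nothing in the plan restores embolizations, removals or early deaths. For failed implants, 10.6.2 and 5.4.6 conflict.

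The direction of the bias in the test-arm rate is certain: upward. Its effect on the error rate is conditional. If HELEX retains such failures, false non-inferiority exceeds the planned 5%, reaching 8.2% to 27.6% from a base of 135 for f of 1% to 5%. If HELEX excludes them as well, the error is not inflated, but the comparison is of something other than the composite in 3.2.1. Confidence in the size is moderate, because it rests on redacted counts and an assumed f. The change should be made before the final analysis, since it settles the primary denominator.

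**What to change.** 1. Amend 10.6.2 and 10.6.3 so that every otherwise eligible enrolled subject with a known component failure (unsuccessful implant, SAE through day 30, or device event through 6 months) stays in the primary denominator as a failure, with or without a 6-month echo. Only subjects with no known failure and no 6-month status are not evaluated. Excluding eligibility violators need not change.
2. Reconcile this wording with 5.4.6.
3. State how a death between day 31 and day 180 is scored, since death is not a named component.
4. Confirm and report that the 253 HELEX subjects are scored by the same rule, and re-score them if not.
5. As a sensitivity analysis, run the same test on the intent-to-treat population with missing counted as failure on both sides (HELEX about 219/271 = 80.8%).

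The cost is a few sentences, one extra analysis and a check, possibly a re-scoring, of the HELEX data. No new test-arm data are needed. The reported success rate may be somewhat lower.
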